8.5 Inclusion and Exclusion Criteria

Patient eligibility for enrollment will be based on known information at the time of the procedure. Information obtained at a later date may contradict these criteria, but this will not be considered a violation of the Clinical Investigation Plan. [Information has been redacted due to confidential content.]

Inclusion Criteria:

- 1) symptomatic venous outflow obstruction in one iliofemoral venous segment (i.e., one limb) per patient, demonstrated by:
 - CEAP “C” ≥ 3 , or
 - VCSS pain score ≥ 2

General Exclusion Criteria:

- 1) < 18 years of age;
- 2) pregnant or planning to become pregnant in the next 12 months;
- 3) surgical or interventional procedures of the target limb (except thrombolysis and/or thrombectomy in preparation for the procedure or vena cava filter placement prior to stent implantation in patients at high risk for pulmonary embolism) within 30 days prior to the study procedure;
- 4) surgical or interventional procedures for other medical conditions (i.e., not associated with the target limb) within 30 days prior to the study procedure;
- 5) lesions with intended treatment lengths extending into the inferior vena cava or below the level of the lesser trochanter;
- 6) lesion with malignant obstruction;

- 7) previous stenting of the target vessel; and

Venographic Exclusion Criterion:

- 1) iliofemoral venous segment unsuitable for treatment with available sizes of study devices.

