8.7.6 Follow-up Schedule

Follow-up windows are intended as guidelines only. They are not absolute and are not intended to limit data collection due to scheduling conflicts.

- *1-month clinic visit (30 days ± 5 days):* An office visit will be completed including documentation of VDS, CEAP “C” Classification, CIVIQ, and VCSS scores, and assessment of medications, hospitalizations and medical conditions.
- *3-month telephone contact (90 days ± 10 days):* Patients will be contacted by telephone by the investigative site for clinical evaluation and assessment of hospitalizations and medical conditions. Up to three attempts should be made to contact the patient.
- *6-month clinic visit (180 days ± 30 days):* An office visit will be completed including documentation of VDS, CEAP “C” Classification, CIVIQ, and VCSS scores, and assessment of medications, hospitalizations and medical conditions. Duplex ultrasound of the treated venous segment (including the cranial and caudal vessel segments) to assess clinical patency and 2 view stent x-ray (both obliques of the pelvis recommended) to assess device integrity will be performed. Confirmatory venography in approximately two orthogonal views will be performed if the patient is symptomatic and the ultrasound is inadequate to assess clinical patency.
- *12-month clinic visit (365 days ± 45 days):* An office visit will be completed including documentation of VDS, CEAP “C” Classification, CIVIQ, and VCSS scores, and assessment of medications, hospitalizations and medical conditions. Venography in approximately two orthogonal views will be performed of the treated segment and at least 1 cm cranial and caudal to the treated segment to assess quantitative patency. A calibration source (e.g., LeMaitre Ruler) will be in the field of view, but not overlapping the vessel. Duplex ultrasound of the treated venous segment (including the cranial and

caudal vessel segments) to assess clinical patency, and 2 view stent x-ray (both obliques of the pelvis recommended) to assess device integrity will be performed.

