- *24-month clinic visit (730 ± 60 days):* An office visit will be completed including documentation of VDS, CEAP “C” Classification, CIVIQ, and VCSS scores, and assessment of medications, hospitalizations and medical conditions. Duplex ultrasound of the treated venous segment (including the cranial and caudal vessel segments) to assess clinical patency and 2 view stent x-ray (both obliques of the pelvis recommended) to assess device integrity will be performed. Confirmatory venography in approximately two orthogonal views will be performed if the patient is symptomatic and the ultrasound is inadequate to assess clinical patency.
- *36-month clinic visit (1095 ± 75 days):* An office visit will be completed including documentation of VDS, CEAP “C” Classification, CIVIQ, and VCSS scores, and assessment of medications, hospitalizations and medical conditions. Duplex ultrasound of the treated venous segment (including the cranial and caudal vessel segments) to assess clinical patency and stent 2 view x-ray (both obliques of the pelvis recommended) to assess device integrity will be performed. Confirmatory venography in approximately two orthogonal views will be performed if the patient is symptomatic and the ultrasound is inadequate to assess clinical patency.

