Occlusion, Early – No flow within the treated venous segment (including the region within ± 1 cm proximal and/or distal to the treated venous segment) occurring ≤ 24 hours of the procedure as demonstrated by duplex ultrasound or venography. An occlusion occurring within 24 hours of the procedure will be considered thrombotic in nature, regardless of whether it is successfully treated with thrombolysis/thrombectomy.

Occlusion, Intermediate – No flow within the treated venous segment (including the region within ± 1 cm proximal and/or distal to the treated venous segment) occurring > 24 hours after the procedure, but ≤ 30 days after the procedure as demonstrated by duplex ultrasound or venography. An occlusion occurring within 30 days of the procedure will be considered thrombotic in nature, regardless of whether it is successfully treated with thrombolysis/thrombectomy.

Occlusion, Late – No flow within the treated venous segment (including the region within ± 1 cm proximal and/or distal to the treated venous segment) occurring > 30 days after the procedure as demonstrated by duplex ultrasound or venography.

Outflow Obstruction – Documented iliofemoral venous obstruction (e.g., recanalization of the vein with multiple channels, documented collaterals as determined by imaging).

Patency, Clinical – Lack of occlusion of the treated venous segment determined by evidence of blood flow both proximal and distal to the study lesion assessed via ultrasound and/or venography and no worsening of pain or edema symptoms from baseline (according to Venous Clinical Severity Score; VCSS) as related to the target lesion.

Patency, Quantitative – A treated venous segment (including the region within ± 1 cm proximal and/or distal to the treated venous segment) minimum lumen diameter $> 50\%$ of the immediate post-procedure stented minimum lumen diameter as demonstrated by venography.

Patency, Primary Quantitative – A treated venous segment retains primary quantitative patency provided that uninterrupted (intervention-free) quantitative patency remains since the initial procedure as determined by the core laboratory. Failure of primary quantitative patency occurs at the time of one of the following: loss of quantitative patency, occlusion of the treated segment, surgical bypass of the treated segment, or amputation of the extremity determined to result from venous outflow occlusion.

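### Clinical patency is tested by flow above and below the lesion, but occlusion means no flow inside the segment, so an occluded segment can be recorded as clinically patent

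*Combined protocol and SAP*

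**What the plan says.** - **Clinical patency (Appendix B).** Two conditions must both hold. The imaging condition is "Lack of occlusion of the treated venous segment determined by evidence of blood flow both proximal and distal to the study lesion", judged by ultrasound, venography or both. The symptom condition is "no worsening of pain or edema symptoms from baseline", scored on the VCSS and related to the target lesion.
- **Occlusion (Appendix B).** The early, intermediate and late forms share one criterion: "No flow within the treated venous segment", with 1 cm at either end included, shown by duplex or venography.
- **Collaterals (Appendix B).** The definition of outflow obstruction gives "documented collaterals as determined by imaging" as an example of evidence. Procedural success looks, in part, for less flow through collateral veins.
- **Schedule (section 8.7.6).** At 6, 24 and 36 months duplex is done "to assess clinical patency and 2 view stent x-ray" for device integrity. Venography is added at those visits only if the patient has symptoms and the scan is not good enough to judge clinical patency. At 12 months all patients have both duplex and venography: "Venography in approximately two orthogonal views will be performed of the treated segment and at least 1 cm cranial and caudal".
- **Duplex coverage (Table 8.1, footnote d).** The scan must take in the treated segment itself as well as the vessel above and below it.
- **Baseline (section 8.5).** Patients enter with "symptomatic venous outflow obstruction in one iliofemoral venous segment (i.e., one limb) per patient", shown by CEAP class C3 or higher or by a VCSS pain score of at least 2.

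**The concern.** The two definitions should be complements, because clinical patency is described as the lack of occlusion. They are not, because they look for flow in different places. Occlusion is about the inside of the segment; the test named for clinical patency is about the vessel on either side. In venous disease with collaterals, which the plan itself expects, flow on both sides does not show flow through the stent.

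At stake is the scheduled duplex read of clinical patency, above all after 12 months, when routine venography has ended. Two readers who both follow the text could classify the same scan differently, and the disagreement can only raise the reported patency. The same duplex could also show an occlusion, which Appendix B counts as a failure of primary quantitative patency, and be filed as clinically patent.

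**Working it through.** The point turns on wording, so the check sets the definitions beside each other.

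1. **Can one segment meet both definitions?** Take a segment with no flow inside it or within 1 cm of either end, and with flow farther up and farther down.
   - Occlusion asks about flow inside the segment and its margins. There is none, so the segment is occluded.
   - The clinical patency flow test asks about flow proximal and distal to the lesion. Both are present, so the stated test is passed.

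2. **Is that state foreseeable?** Yes. Appendix B treats collaterals as evidence of obstruction. Section 8.7.4 takes the outflow tract from just above the lesion to the L1 level of the inferior vena cava, and only one limb is treated (section 8.5). For a lesion near the confluence, flow above it can come from the other limb.

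3. **Does the symptom condition catch it?** Only in part. Worsening is counted from the pre-procedure score, when the patient was symptomatic. A patient who enters with VCSS pain 2, falls to 0 after stenting and returns to 2 on re-occlusion has a change from baseline of 2 − 2 = 0, which is not worsening. Edema is judged in the same way. A patient who passes the baseline level on either item is caught. After a reintervention other than bypass, section 8.7.8 stops VCSS collection while imaging continues to 36 months; the text does not say how the symptom condition is then judged.

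4. **At which visits does it matter?**

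| Visit | Scheduled duplex for clinical patency | Venography of the treated segment |
|---|---|---|
| 6 months | Yes | Only if symptomatic and scan inadequate |
| 12 months | Yes | All patients |
| 24 months | Yes | Only if symptomatic and scan inadequate |
| 36 months | Yes | Only if symptomatic and scan inadequate |

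At 12 months the venogram should show the occlusion. The definition accepts either modality, though, and does not say which one counts if they differ.

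5. **Does it touch the primary analysis?** No. The planned numbers reproduce without it: 218 / (1 − 0.10) = 242.2, rounded up to 243. An exact one-sided binomial test at 0.025 with 218 patients gives:
   - effectiveness: success at 179 or more (82.1%), attained level 0.0186, power 0.956 at a true rate of 86% against the 76% goal;
   - safety: success at 200 or more (91.7%), attained level 0.0192, power above 0.999 at a true rate of 97% against the 87% goal.

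   Both exceed the stated minimum of 0.90. Section 9.2 obtains 218 by simulation and leaves the details to the SAP, so only that minimum could be checked. Clinical patency enters none of these figures.

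6. **Direction and size.** The overstatement at a visit is (share occluded) × (share of those with flow at both ends) × (share of those with pain and edema no worse than baseline) × (share read by the flow test rather than by the occlusion definition). Every factor is zero or positive, so the error can only raise clinical patency. The documents give none of the four.

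**The case against.** **The opening term protects the definition.** It begins with lack of occlusion, and occlusion is defined in the same appendix. A reader who sees no flow inside the segment, on a scan that must cover it, may simply call it occluded. This stands, and it is why the segment *can be* recorded as patent; a reader might infer that it *will be*, and the text does not support that. But the definition goes on to name how lack of occlusion is determined, and that test never looks inside the segment.

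**The flow sites may lie inside the stent.** The clinical patency test refers to the lesion, section 8.7.4 has the stent reach 5-10 mm past it at each end, and the occlusion definitions add 1 cm. Flow sampled very close to the lesion would then be flow within the segment. This is fair, but the definition gives no distance and the duplex also covers the vessels above and below, so sampling farther away is allowed.

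**Stronger readings that the documents do not support.**
- *A false patent read causes venography to be skipped.* The trigger is symptoms together with an inadequate scan, not the patent or occluded result. An adequate scan read as occluded would not trigger it either.
- *A patient who starts at the top pain score cannot worsen.* Such a patient can still worsen on edema.
- *The primary result is biased.* That endpoint rests on core-laboratory venography and counts occlusion as failure. Section 9.5 lets investigator measurements and clinical sequelae stand in for missing core-laboratory data, but it does not name clinical patency as a substitute.
- *Patency is overstated by a known amount.* Assuming 5-15% of segments occluded and 50-100% of those with flow at both ends gives 0.05 × 0.5 = 2.5 points to 0.15 × 1.0 = 15 points. Both inputs are guesses, and the last two factors in step 6 are set to 1. The 15% ceiling also exceeds the 100 − 86 = 14% loss of quantitative patency from all causes that the plan assumes at 12 months.

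**The role of clinical patency cannot be seen.** It is neither a primary nor a secondary endpoint, the additional measures are redacted, and the Imaging Manual is not supplied. The manual may contain a stricter reading rule. This limits what can be said about consequences, but it does not reconcile two definitions that conflict in the governing text.

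**Conclusion.** The point holds as a conflict between definitions. A segment with no internal flow but with collateral or contralateral inflow at both ends can meet the occlusion definition and be recorded as clinically patent, provided pain and edema are no worse than at the symptomatic pre-stent baseline. The exposure is mainly at 6, 24 and 36 months. At 12 months venography in every patient largely removes it, apart from the unstated rule for discordant results.

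The error has one direction, favourable to the device, and no size that the documents allow one to state. The conclusion assumes that a reader may apply the flow test as written, and that no stricter rule in the Imaging Manual overrides it. The primary endpoint test, performance goal and sample size stand as planned. The change should be made because it is cheap and removes a favourable bias from the durability read, not because study success depends on it.

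**What to change.** Reconcile the definitions in Appendix B:

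1. Make the clinical patency flow test evidence of blood flow inside the treated segment, ±1 cm, on duplex or venography.
2. State that any segment meeting an occlusion definition is not clinically patent, whatever the flow above and below it.
3. State which modality prevails when duplex and venography disagree, which matters most at 12 months, when both are done.

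The symptom condition can stay as it is; measuring change from the pre-procedure baseline is a legitimate choice and matches the secondary VCSS endpoint.

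The cost is a small change to the definition and to the ultrasound reading form. No new imaging is needed, because the duplex already has to cover the treated segment. Reported clinical patency may fall slightly.

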4.2.2 Primary Effectiveness Hypothesis

The primary effectiveness endpoint is 12-month primary quantitative patency, and will be analyzed based on the intent-to-treat population. The analysis requires that the performance goal

(π_{PGE}) of 76% be met for primary quantitative patency at 12 months. The performance goal was derived based on 12-month patency data available in published literature describing patients treated with commercially available stents for acute and chronic iliofemoral venous outflow obstruction.¹⁻³⁹ Patency outcomes were similar among patients with acute and chronic disease. The effectiveness of the Zilver[®] Vena[™] Venous Stent will be established provided the null hypothesis is rejected in favor of the alternative hypothesis with the Binomial test for one proportion at the Type I error level of 0.025.

Let π_E (where E stands for effectiveness) be the probability that a randomly selected patient's treated segment is primary patent (quantitative) at 12 months, then the hypothesis is formulated as follows:

Null Hypothesis: The 12-month primary quantitative patency for patients treated with the Zilver[®] Vena[™] Venous Stent does not meet the performance goal (76%).

$$H_0: \pi_E \leq \pi_{PGE}; \text{ or } H_0: \pi_E \leq 76\%$$

Alternate Hypothesis: The 12-month primary quantitative patency for patients treated with the Zilver[®] Vena[™] Venous Stent meets the performance goal (76%).

$$H_a: \pi_E > \pi_{PGE}; \text{ or } H_a: \pi_E > 76\%$$

Study success requires that both primary hypotheses (i.e., safety and effectiveness) be met.

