9.5 Missing Data

Missing data will be addressed using two primary strategies: 1) multiple imputation with best available data, if appropriate, and 2) case deletion. The first strategy is multiple imputation with best available data, if appropriate. This method will be used to predict missing endpoint and imaging data. Previous clinical trial experience suggests that some portion of the imaging data may not meet the criteria for accurate review by the core laboratory; however, it is recognized that the investigator uses this information to provide the best possible care for the patient. Therefore, it is reasonable to substitute any missing core laboratory measurements with the corresponding measurements made by the investigator or institutional staff. In addition, the absence or presence of clinical sequelae may supplement the required missing core laboratory assessment of device performance. This strategy is a best approximation of the missing data value.

Statistical imputation strategies originating from Schafer⁴⁰ may also be used, supplemented with notes provided by Schafer.⁴¹ The computations (with no covariates) will be performed using PROC MI and PROC MIANALYZE in SAS version 9.3 or later, or WinBUGS 1.4 or later. Unless evidence suggests otherwise, missing at random data will be assumed.

The second strategy is case deletion. If the amount of missing data does not result in a reduction of analyzable patients to a number that is below that which is required for sufficient statistical power of the primary endpoints, then case deletion will be the method of choice for that analysis.

Additional analyses may also be performed to address missing data, including tipping point analysis.

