Patency, Assisted Primary Quantitative – A treated venous segment retains assisted primary quantitative patency if, following successful treatment at the initial procedure, the segment subsequently requires an intervention to assist quantitative patency without an episode of occlusion. Failure of primary assisted quantitative patency occurs at the time of one of the following: total occlusion of the treated segment, surgical bypass of the treated segment, or amputation of the extremity determined to result from venous outflow occlusion.

Patency, Secondary Quantitative – A treated venous segment retains secondary quantitative patency if, following successful treatment at the initial procedure, the segment subsequently becomes totally occluded and then successfully reopened in a secondary procedure. Failure of secondary quantitative patency occurs at the time of surgical bypass of the treated segment or amputation of the extremity determined to result from venous outflow occlusion.

Pulmonary Embolism (PE) – Emboli to lungs via the pulmonary artery, which can arise from deep venous thrombosis in the lower extremities or pelvis. Pulmonary emboli should be objectively documented using pulmonary arteriography, cross-sectional imaging, or significant change in ventilation/perfusion lung scan indicative of PE, or at autopsy. PE will be categorized by type.^c

Pulmonary Embolism (PE), Massive – Acute PE with sustained hypotension (systolic blood pressure < 90 mmHg for at least 15 minutes or requiring inotropic support, not due to a cause other than PE, such as arrhythmia, hypovolemia, sepsis, or left ventricular [LV] dysfunction), pulselessness, or persistent profound bradycardia (heart rate < 40 bpm with signs or symptoms of shock).

Pulmonary Embolism (PE), Submassive – Acute PE without systemic hypotension (systolic blood pressure ≥ 90 mmHg) but with either right ventricular (RV) dysfunction or myocardial necrosis, where:

RV dysfunction is defined as the presence of at least 1 of the following:

- RV dilation (apical 4-chamber RV diameter divided by LV diameter > 0.9) or RV systolic dysfunction on echocardiography;
- RV dilation (4-chamber RV diameter divided by LV diameter > 0.9) on CT;
- Elevation of BNP (> 90 pg/mL);
- Elevation of N-terminal pro-BNP (> 500 pg/mL); or
- Electrocardiographic changes (new complete or incomplete right bundle-branch block, anteroseptal ST elevation or depression, or anteroseptal T-wave inversion).

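### Read literally, section 9.5 would delete ITT patients with no study stent deployed from the 12-month patency test, and the supplied text gives no rule for scoring them

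*Combined protocol and SAP*

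**What the plan says.** Section 4.2.2 names the population: "The primary effectiveness endpoint is 12-month primary quantitative patency, and will be analyzed based on the intent-to-treat population". The test is a one-proportion binomial test at 0.025 with alternative above 76%. The 76% goal was "derived based on 12-month patency data available in published literature describing patients treated with commercially available stents".

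Section 8.6 places ITT entry at introduction of the delivery system, before deployment. Section 8.9 foresees failure to deploy and ends participation 30 days afterwards. That covers the 30-day safety endpoint but not the 12-month venogram of section 8.7.6.

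Appendix B defines quantitative patency as a minimum lumen diameter above 50% "of the immediate post-procedure stented minimum lumen diameter as demonstrated by venography". Primary quantitative patency is retained if "uninterrupted (intervention-free) quantitative patency remains since the initial procedure as determined by the core laboratory", and it fails on "loss of quantitative patency, occlusion of the treated segment, surgical bypass of the treated segment, or amputation of the extremity" (the amputation being one caused by venous outflow occlusion). Assisted primary patency carries a condition: "following successful treatment at the initial procedure, the segment subsequently requires an intervention to assist quantitative patency". Secondary patency carries the same condition of successful initial treatment. The primary definition neither has that condition nor says how an unsuccessful initial treatment is scored. Technical success is defined separately and not tied to patency.

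Section 9.5 names two routes for missing data: multiple imputation with best available data, and case deletion. If enough analyzable patients remain for power, "then case deletion will be the method of choice for that analysis". The imputation computations use no covariates and assume missing at random unless evidence suggests otherwise. Section 9.5 also says that "the absence or presence of clinical sequelae may supplement the required missing core laboratory assessment of device performance".

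**The concern.** An ITT patient without a stent has no 12-month venogram and no denominator for the patency ratio, and non-deployment is not a listed failure event. The nearest explicit rule is section 9.5, and its preferred method removes the patient. The alternative, imputation without covariates under missing at random, fills the gap from the patency rate of patients who were stented. Neither route obliges the analyst to count the patient as a non-success.

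In a single-arm trial against a fixed goal, the denominator feeds straight into the verdict. Removing patients in whom the device was not delivered moves the estimate in the device's favour relative to the ITT quantity that section 4.2.2 names. The result would describe stented patients under an ITT label.

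**Working it through.** **Inputs from the protocol.** Goal 76%, binomial test at 0.025, one-sided alternative (section 4.2.2). Required number 218, 10% allowance, enrollment 243, assumed patency 86%, minimum power 0.90 (section 9.2).

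**The plan's own figures.** 218 / 0.90 = 242.2, rounded up to 243, as stated. With a fixed exact test at n = 218, success needs 179 patent patients (attained level 0.0186) and power at 86% is 0.956, consistent with the stated minimum. If 218 is the number that section 9.5 requires for power, deletion stays available for up to 243 − 218 = 25 patients from all causes.

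**Assumption.** Let k be the number of ITT patients with no study stent. The documents give no value; k = 0, 1, 2 and 5 are used.

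**Formulas.** The critical count c(n) is the smallest c with P(X ≥ c | n, 0.76) ≤ 0.025. If true ITT patency is exactly 76%, with the k patients counted as non-successes, patency among the stented is p(k) = 0.76 × 243 / (243 − k). With X ~ Bin(243 − k, p(k)):
- deleted: P(X ≥ c(243 − k));
- scored as failures: P(X ≥ 198), since c(243) = 198.

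The last column takes patency among the stented as exactly 76%, so X ~ Bin(243 − k, 0.76), with deletion.

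| k | n analyzed if deleted | c(n) | p(k) | Type I, deleted | Type I, scored as failures | Stented rate 76%, deleted |
|---|---|---|---|---|---|---|
| 0 | 243 | 198 | 76.0% | 0.025 | 0.025 | 0.025 |
| 1 | 242 | 198 | 76.3% | 0.024 | 0.024 | 0.018 |
| 2 | 241 | 197 | 76.6% | 0.033 | 0.023 | 0.020 |
| 5 | 238 | 195 | 77.6% | 0.061 | 0.021 | 0.017 |

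At k = 5, deletion lowers the bar from 198 to 195 patent patients: 195/238 = 81.9% of those analyzed, but 195/243 = 80.2% of ITT.

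**Sharing the loss margin.** Suppose 25 patients in all are not analyzable, k of them undeployed and the rest lost at random, so X ~ Bin(218, p(k)). Deletion, P(X ≥ 179), gives 0.024, 0.031 and 0.062 at k = 1, 2 and 5. Scoring as failures, P(X ≥ c(218 + k)) with critical counts 180, 180 and 183, gives 0.016, 0.021 and 0.013. The pattern is the same.

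**Imputation.** No-covariate imputation under missing at random draws on the observed patency rate, so its expected estimate equals the deletion estimate.

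**The case against.** **The text allows other readings.** Retained patency requires a core-laboratory finding of uninterrupted quantitative patency. A patient with no stented lumen cannot meet that, so could be called a non-success rather than a missing value. Section 3.0 equates the treated segment with the study lesion, so an occluded unstented lesion might count as an occlusion; a non-occluded one would not. Section 9.5 lets clinical sequelae supplement a missing assessment, makes imputation conditional on its being appropriate, and mentions tipping point analysis. All of this stands, but it permits failure scoring without requiring it.

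**The target may be stented patients.** The goal comes from literature on patients treated with stents, and both effectiveness hypotheses in section 4.2.2 are worded in terms of patients treated with the device. Under that target deletion inflates nothing, as the last column of the table shows. This also stands. The analysis would then not be the ITT analysis that the same section names, so the text still has to choose.

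**k may be very small.** Venography of the inflow, outflow and lesion precedes enrollment (section 8.7.4), anatomy unsuitable for the available sizes is excluded (section 8.5), and access failures before the delivery system is introduced never enter ITT. This limits the size of the problem but does not supply a rule.

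**Stronger inferences that the documents do not support.** A reader might infer that the trial has no scoring rule at all. Section 9.1 places full endpoint analyses in a separate statistical analysis plan that is not in the supplied text, so only the silence of that text is established. A reader might also infer that the handling could be picked once results are known. Section 8.3 commits to a prospectively defined analysis plan, and nothing shown contradicts that. Nor can a large error inflation be asserted: it would need many undeployed patients, and the documents give no basis for such a number.

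**Conclusion.** The point holds for the supplied text and should be fixed. ITT patients with no study stent have no explicit score for the primary effectiveness endpoint, and the literal route through section 9.5 would remove them from a test declared to be ITT.

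For the ITT target, handling makes no difference at k = 0 or 1. Under deletion, Type I error is 0.033 at k = 2 and 0.061 at k = 5; scoring as failures keeps it at or below 0.025. For a target of patency among stented patients there is no inflation, only a mismatch with the stated population.

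The figures rest on an assumed k, on all other patients being evaluable (or lost at random in the second calculation), and on a fixed exact test. Section 9.2 refers to a simulated Bayesian adaptive design whose rules are not shown, so these are illustrations and not this trial's operating characteristics. Confidence is moderate, chiefly because the separate analysis plan may already settle the matter.

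**What to change.** Add one sentence to section 9.5 and one clause to the primary quantitative patency definition in Appendix B: in the primary ITT analysis, an ITT patient without successful deployment of the study stent is a primary-patency non-success and is neither deleted nor imputed. Report the successfully stented population as a sensitivity analysis. If the separate statistical analysis plan already says this, a cross-reference is enough.

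No new data are needed. The price is a slightly lower observed rate and some power. If 86% holds only among stented patients, so that X ~ Bin(243 − k, 0.86), power with failures scored is 0.961 at k = 2 (0.974 if deleted) and 0.908 at k = 5 (0.968 if deleted), and the loss grows with k. If 86% is already the ITT rate, power at 243 patients is at least 0.980.
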